3.4 Provider Surveys

We will conduct surveys of cardiology providers after the implementation of the EHR-based alerts across all NYULH Cardiology locations. The survey will aim to obtain further understanding of provider real-world experiences with, and perception of the clinical decision support tools. We will use a mix of likert-scale, multiple-choice, and open-ended questions to assess the alerts based on previously reported implementation science frameworks, specifically focusing on acceptability, usefulness, and ease of use of the two EHR-based alerts.

The goal for this survey is to obtain an overall assessment of the EHR-based alerts' usefulness as a long-term strategy for health system-wide quality improvement. Past evidence suggests that physicians dislike clinical decision support tools, believing they have minimal utility and result in general inefficiency, increased time required for care, and contribute to a sense of alert fatigue. We seek to determine whether these perceived downsides of EHR-based alerts were a factor in providers' impressions of the alerts used in this study. . The final survey is attached.

4 Study Population

4.1 Total Number of Participants and Sites

This is a single site study involving NYULH outpatient cardiology clinics serving a total of approximately 2000 participants.

4.2 Inclusion Criteria

- Patient with an encounter visit at NYULH cardiology practice during the study period
- Patient with EF \leq 40% on most recent echocardiogram
- Patient ages 18-100

4.3 Exclusion Criteria

- Pregnancy
- Ventricular assist device
- In order to give providers time to add and up-titrate medications, we will exclude patients who had a newly reduced EF in the last 3 months.
- Medication-specific exclusion for MRA: most recent systolic blood pressure less than 105 mm Hg, most recent potassium < 5.1, any potassium > 5.5, most recent glomerular filtration rate < 30 (using MDRD equation), or a documented MRA allergy.

CONFIDENTIAL

This material is the property of the NYU School of Medicine and Langone Health. Do not disclose or use except as authorized in writing by the study sponsor

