1.1 Background Information and Relevant Literature

For patients with heart failure and reduced ejection fraction (HFrEF), the cornerstone of evidence-based care includes several medications that have been found to significantly reduce morbidity and mortality, which include: 1) mineralocorticoid antagonists (MRA), 2) angiotensin converting enzyme inhibitors, angiotensin receptor blockers, angiotensin receptor neprilysin inhibitors (ACE-I/ARB/ARNI), and 3) beta-blockers (BB). Current guidelines give these medications a class I recommendation,¹ and recently published performance measures² also strongly recommend these agents. However, despite their well-accepted benefits, several prior studies have revealed significant gaps in medical therapy for HFrEF patients.³⁻⁵ Using number-needed-to-treat estimates based on data from randomized trials, these gaps in medical therapy account for an estimated 68,000 deaths per year nationwide, with the largest proportion being from lack of appropriate MRA therapy.⁶

In prior studies, successful interventions for improvement have often included multidisciplinary approaches with nurses, pharmacists, or other trained individuals.⁷⁻⁹ However, the need for dedicated staff can be costly, and electronic health record (EHR)-based interventions could be a potential cost-effective solution. Prior studies assessing the efficacy of EHR-based interventions to improve medical therapy for HFrEF have mainly been conducted in the inpatient setting.¹⁰⁻¹² Inpatient algorithms may be limited as they reflect one instance in time. Additionally, acute hospitalization may restrict the ability to add multiple agents due to renal dysfunction or hypotension. Therefore, we propose the development of an outpatient EHR-based system to target patients with HFrEF who are not on the appropriate therapy.

Outpatient provider-facing EHR-based interventions could include best practice alerts (BPA) or electronic messages. While limited data exist for both types of interventions, some studies have observed significant improvements in health outcomes.¹³⁻¹⁵ Potential adverse effects have also been described, such as increased alert frequency with BPAs¹⁴ and physician burnout with electronic messages.¹⁶ Given the potential for benefit and/or harm, it is imperative to study such interventions with rigor. Currently, no study directly compares different types of EHR-based alerts.

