3.2 Intervention

The two types of EHR-based alerts include: 1) BPA and 2) electronic message.

CONFIDENTIAL

This material is the property of the NYU School of Medicine and Langone Health. Do not disclose or use except as authorized in writing by the study sponsor

Best Practice Alert (BPA) – BPAs are alerts that appear at the time of the visit, allowing for real-time intervention while the provider is with a patient, but also potentially interrupting provider workflow. The BPA appears at the beginning of a visit/encounter and includes 1) a tailored advisory, 2) educational link to guidelines, 3) medication information, 4) vital sign and pertinent lab results, and 5) options for next steps (i.e. ordering medication, providing reasons for not prescribing).

Electronic Message – Unlike the BPA, the electronic message is not necessarily seen at the time of the visit, and is more likely to be seen between visits. The electronic message is similar to the BPA in terms of information provided, but can include information on multiple patients in the same message, and overall prescribing metrics.

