4.4 Vulnerable Subjects

No vulnerable patients will be enrolled.

For the survey, we will recruit NYULH cardiologists who received the BPAs or messages. The only way to obtain feedback on the BPAs and electronic messages is from the cardiologists at NYULH who received the BPAs and electronic messages, as they are the only ones who can comment on the acceptability, usefulness, and ease of use of these EHR tools. Cardiologists will be informed that their decision to participate or not, and their responses, will in no way affect their employment, salary, or performance evaluations and they will be reminded that they can stop participating whenever they want. Their information will be de-identified and completely anonymous. No identifiable PII or health information will be collected.

5 Strategies for Recruitment

Eligible patients from the chosen practice sites will be identified electronically within EPIC using an algorithm developed by the study team and NYULH's DataCore. This algorithm reviews patient records for $EF \leq 40\%$ on most recent echocardiogram, and exclusion criteria listed above. Patients meeting eligibility will be automatically included, and all data collection will take place passively via the NYULH EHR system, EPIC. An EPIC reporting analyst will extract the relevant parameters from EPIC into a report. Patients from the selected practice sites will undergo their usual interactions with their providers and no study-specific activities will take place.

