5.3 Provider Survey Recruitment

For the provider survey, we will recruit cardiologists who received the BPA or electronic message through emails (see attachment). They will be made aware that completing the survey is completely anonymous and will in no way impact their employment. The recruitment emails will be sent via listservs of cardiologist who received the BPAs and electronic messages. These listservs are specific for those cardiologists who received BPAs or electronic messages and the survey does not require cardiologists to self-select whether they received a BPA or a message. Only cardiologists who received a BPA or electronic message will be contacted. We will send an initial recruitment email and a subsequent follow up email.

The consent form will be attached to the email. It will also be available via link within the first question in Qaltrix. The first question in Qaltrix asks the provider to review the consent document and requires the provider to click a button stating that they are consenting to participate before being shown the remaining survey questions. If the provider does not click this button, they will not be able to move forward or complete the survey.

6 Study Schedule

Participants will be included in this study by virtue of meeting eligibility criteria and having a patient encounter during the study period. There are no study-specific visits. Any patient meeting criteria who has one or more patient encounters during the study period will be included. Therefore, no study-specific visits are relevant for this study, so there is no schedule of visits.

CONFIDENTIAL

This material is the property of the NYU School of Medicine and Langone Health. Do not disclose or use except as authorized in writing by the study sponsor

7 Study Procedures / Evaluations

There are no study-specific procedures that patients will undergo. They will receive care as usual by their outpatient providers. The EHR algorithm developed by the study team identifies eligible patients with EF \leq 40% on most recent echocardiogram, and exclusion criteria listed above. The EHR algorithm will also capture information on demographics, diagnoses in the patient's problem list, prescription history, allergies, EF, and relevant lab results.

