For patients meeting the eligibility criteria, a message in the EHR will automatically be sent to the provider. The provider will receive either a Best Practice Alert (BPA) or electronic message indicating that their heart failure patient is not on guideline-recommended therapy. The message will offer guidance for physician decision-making regarding HFrEF care. The study team presented the proposed project to the NYULH MCIT Project Portfolio Review Committee on February 11, 2021 and was approved to work with MCIT to build the electronic messages. Providers will be notified through the Weekly Epic Update and in presentations to medical directors that they may see the alert prior to the start of the study.

Patients' clinical outcomes will be monitored through EHR data collection for 18 months. Data collection will include elements of protected health information including patient name, medical record number, address zip code, and service dates. These will be necessary for data linkages and in order to track patients for receipt of intervention and clinical outcomes. All PHI data will be kept on a secure NYULH server and destroyed at the earliest possible point. Data on the patient's medication prescription, hospitalization, hospitalization for HF, and mortality will be recorded as study outcomes. The study team members will not collect this information directly; data will be collected in NYULH's EHR system, EPIC, and an EPIC Reporting analyst from DataCore will extract the relevant parameters from the EHR into a report.

Data points that will be collected for research purposes
Medication prescription
Hospitalization
Hospitalization for HF
Mortality
Name
Medical record number
Address zip code
Service dates

Provider survey data will be anonymously collected via Qualtrix. No identifiable information, PII, or health information will be collected. The URLs for the survey are below:

BPA version = https://nyumc.yul1.qualtrics.com/jfe/preview/previewId/f42fb1cb-b997-4fb8-8f60-9e311e6b6320/SV_7P3UhfVSH6KgpuK?Q_CHL=preview&Q_SurveyVersionID=current

IBM version = https://nyumc.yul1.qualtrics.com/jfe/preview/previewId/c97ab951-3feb-478a-8af8-a53e9abbe02d/SV_7PQoQunPLM8I8ZU?Q_CHL=preview&Q_SurveyVersionID=current

8 Safety and Adverse Events

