11.3 Informed Consent Process

We will obtain a waiver of informed consent and a waiver of HIPAA authorization for patients seen in the participating clinics to acknowledge their participation at a clinic level. The risks to subjects are exactly equivalent to the risks experienced in the standard setting of patient care. The new module to be activated in EPIC relates only to guidance for physician decision-making regarding HFREF care, and has no impact on disclosure or treatment of PHI. Patients will receive care from their providers in the usual way. The only difference is the interface with the electronic health record that is used by the physician during the course of the patient encounter. The autonomy of the provider to make decisions about patient care will not be affected. It is impracticable to obtain consent from patients for receipt of standard medical care by their usual providers. It is unclear what they would be providing consent for, since they will receive care as usual from their providers. Patients will not be provided with additional information. They will be treated as usual by their providers and the providers' experience with the module is irrelevant to their patient experience.

For provider surveys, we are requesting a waiver of documentation of consent. These surveys present no more than minimal risk to providers. Prior to beginning survey questions, providers will be given consent form that contains all pertinent study and contact information. The consent form will be attached to the recruitment email and also will be available via link in Qaltrix prior to the survey. The providers will be asked to acknowledge consent through clicking a button within Qaltrix before they are able to participate in the survey questions. Providers will be informed that they may agree not to participate and that this will have no bearing on their employment status.

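### The MRA potassium exclusion in Section 4.3 is almost certainly printed with its sign reversed: as written, only a latest value of 5.1–5.5 escapes exclusion

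*Combined protocol and SAP*

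**What the plan says.** Section 4.3 (Exclusion Criteria) has one sentence of MRA-specific exclusions, with the items joined by a final *or*, so that any one of them excludes. It opens "Medication-specific exclusion for MRA: most recent systolic blood pressure less than 105 mm Hg", continues "most recent potassium < 5.1, any potassium > 5.5", and ends with a GFR below 30 and a documented MRA allergy. The potassium cut-offs appear nowhere else in the document.

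The list is meant to be executed by software. Section 5 says that the algorithm screens records on ejection fraction "and exclusion criteria listed above. Patients meeting eligibility will be automatically included". Section 7 repeats that the algorithm identifies patients by ejection fraction "on most recent echocardiogram, and exclusion criteria listed above. The EHR algorithm will also capture" further data, and then states: "For patients meeting the eligibility criteria, a message in the EHR will automatically be sent to the provider".

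On the weight of this drug class, Section 1.1 attributes an estimated 68,000 deaths a year to gaps in therapy, "with the largest proportion being from lack of appropriate MRA therapy".

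**The concern.** High potassium is the hazard that the neighbouring clause guards against, yet the clause on the latest value excludes everyone *below* 5.1. Taken literally, the two clauses remove patients with low or normal potassium and keep those just under the protocol's own upper limit. That is the opposite of what an MRA safety screen is for.

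Two things are at stake, depending on the build:

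- **If the algorithm was programmed from the printed text**, the MRA alert would not fire for patients with low or normal potassium. They would get usual care without the intervention under test, in the class where the protocol sees the largest gap. The alerts that did fire would concern patients with a latest value of 5.1–5.5.
- **If the algorithm has the intended direction**, the protocol misstates who was excluded. Anyone auditing, replicating or re-programming from it would get the wrong rule.

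**Working it through.** The plan states no figure on this point, so there is none to reproduce. The check is logical.

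**Inputs (Section 4.3).** Clause A excludes if the latest potassium is < 5.1. Clause B excludes if any potassium is > 5.5. No unit is given. Either clause is enough to exclude.

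**Step 1: apply the rule, with values to one decimal.** A patient stays eligible on potassium only if A and B are both false, that is, latest ≥ 5.1 and every value ≤ 5.5.

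| Latest potassium | As printed | Sign reversed (> 5.1) | Sign reversed (≥ 5.1) |
|---|---|---|---|
| Below 5.1, no value above 5.5 | Excluded by A | Eligible | Eligible |
| Exactly 5.1, no value above 5.5 | Eligible | Eligible | Excluded |
| 5.2–5.5, no value above 5.5 | Eligible | Excluded | Excluded |
| Any latest value, some value above 5.5 | Excluded by B | Excluded | Excluded |
| No potassium recorded | Caught by neither clause | Caught by neither clause | Caught by neither clause |

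Stepping from 3.0 to 6.5 by 0.1 gives 36 possible latest values. As printed, 5 remain: 5.1, 5.2, 5.3, 5.4 and 5.5. With > 5.1 as the exclusion, 22 remain (3.0 to 5.1). With ≥ 5.1, 21 remain (3.0 to 5.0). The printed rule shares one value (5.1) with the first correction and none with the second. These are counts of values, not of patients.

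**Step 2: compare the direction of each clause.**

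| Clause in 4.3 | Side excluded |
|---|---|
| Systolic pressure below 105 | Higher risk (low pressure) |
| Latest potassium < 5.1 | **Lower risk (low and normal potassium)** |
| Any potassium > 5.5 | Higher risk (high potassium) |
| GFR below 30 | Higher risk (poor renal function) |
| MRA allergy | Higher risk |

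One clause of five points the other way, and no reason is given for it. With the sign reversed, the two potassium clauses make a sensible pair: a tighter limit on the current value and a looser one on any value. As printed, they leave a band 5.5 − 5.1 = 0.4 wide.

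**Step 3: trace the effect on Section 9.2.** That section contains two different quantities.

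- The requirement of 501 per arm (3 × 501 = 1503) is stated for 80% power to detect a 10% improvement. Potassium eligibility does not enter it.
- The range of 1500–2000 estimates how many patients will trigger alerts. A patient whose only gap is an MRA would trigger none if clause A wrongly excluded them, so this count could fall. The documents do not say how many such patients there are, or which sign the estimate used. The low end is already 1503 − 1500 = 3 short of the requirement, so there is no slack there.

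**The case against.** The strongest reply is that this is one misprinted character. The clause beside it makes the intent plain to any clinician, the study team helped to develop the algorithm, and all patient-level harm depends on code that the documents do not show. The last part stands: no harm can be asserted. The rest does not dispose of the point. The text is not background. It is the only statement of the rule that the algorithm is said to apply, and that clinical team members would have caught the slip is supposition.

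A second reply is that a sign can be misread when a PDF is converted to text. That cannot be excluded for a symbol that occurs once. However, the other signs in the same sentence read sensibly and nothing points to a misreading. Looking at the source page settles it, so that comes first in the fix.

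A reader might also infer a serious safety hazard, with alerts steering MRAs to patients with dangerous potassium. The documents do not support that. Even under the printed rule, any value above 5.5, a GFR below 30 and a systolic pressure below 105 still exclude. Section 3.2 has the BPA show "vital sign and pertinent lab results, and 5) options for next steps (i.e. ordering medication, providing reasons for not prescribing", with similar information in the electronic message, and Section 11.3 says: "The autonomy of the provider to make decisions about patient care will not be affected".

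**Conclusion.** The point holds. Section 4.3 is wrong as written: among patients with a recorded potassium, only those with a latest value of 5.1–5.5 and no value above 5.5 escape the potassium exclusions. That the sign is reversed is an inference, but a strong one, resting on the direction of every other clause and the absence of any stated reason. It is a wrong operative threshold in an automated intervention and must be corrected whichever way the build turns out.

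The size is that of the logical error. Turning it into a share of patients would need a potassium distribution that the documents do not give, and the conclusion does not depend on one.

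Four further inferences are tempting but not supported:

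- *That alerts actually went to the wrong patients.* The deployed logic is not shown.
- *That the whole of Section 9.2 falls, or that none of it is touched.* The 501 per arm does not depend on this clause; the 1500–2000 estimate may, if the build repeats the sign.
- *That the MRA outcome denominator is distorted.* Section 3.3 does not limit the prescribing outcome to alert-eligible patients.
- *That the IRB reviewed and passed this sign.* Section 11.2 only requires approval before enrolment.

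The *medication-specific* label suggests that beta-blocker and ACE-I/ARB/ARNI advice is untouched, but the documents do not describe separate alerts by drug, so that is also an inference.

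**What to change.** 1. Confirm the sign on the source page of the protocol.
2. Amend Section 4.3 so that the exclusion is a latest potassium > 5.1, or ≥ 5.1. The documents do not fix the boundary, so the clinical lead should confirm which. Obtain IRB approval of the amendment under Section 11.2.
3. Check the direction of this clause in the EHR logic.
4. If the build repeats the printed sign, correct it, record the dates affected, and re-run both the MRA-eligible count and the Section 9.2 estimate of 1500–2000 patients triggering alerts, since patients missing only an MRA would have been left out.
5. If the build has the intended sign, document that only the text was wrong.

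The 501 per arm needs no change on this account. The cost is a one-line amendment with IRB review and one check of the build logic, plus a re-run of two counts if the build repeats the sign.

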4.4 Vulnerable Subjects

No vulnerable patients will be enrolled.

For the survey, we will recruit NYULH cardiologists who received the BPAs or messages. The only way to obtain feedback on the BPAs and electronic messages is from the cardiologists at NYULH who received the BPAs and electronic messages, as they are the only ones who can comment on the acceptability, usefulness, and ease of use of these EHR tools. Cardiologists will be informed that their decision to participate or not, and their responses, will in no way affect their employment, salary, or performance evaluations and they will be reminded that they can stop participating whenever they want. Their information will be de-identified and completely anonymous. No identifiable PII or health information will be collected.

5 Strategies for Recruitment

Eligible patients from the chosen practice sites will be identified electronically within EPIC using an algorithm developed by the study team and NYULH's DataCore. This algorithm reviews patient records for $EF \leq 40\%$ on most recent echocardiogram, and exclusion criteria listed above. Patients meeting eligibility will be automatically included, and all data collection will take place passively via the NYULH EHR system, EPIC. An EPIC reporting analyst will extract the relevant parameters from EPIC into a report. Patients from the selected practice sites will undergo their usual interactions with their providers and no study-specific activities will take place.

